### **Day of Cardiac Ablation**

After the baseline visit, patients will be scheduled for a cardiac ablation. Clinical investigators will schedule ablation procedures within 90days after CMR imaging has been completed.

Patients will be medically assessed by the site investigator. Patients who are deemed by the site investigator to have not tolerated the ablation well will not be enrolled in the study. Due to current hospital SOC, patients may be discharged up to 24 hours after ablation. Discharge may be expedited per physician discretion and other hospital-based policies (e.g. COVID-19, etc.).

### ***Biometric Equipment***

#### ***BodyGuardian® MINI Plus EL (ECG monitoring device)***

Patients will receive an FDA-approved BodyGuardian® MINI Plus EL ECG monitoring device kit provided by Preventice Solutions. The patients will be educated on how the monitor works and will be instructed to wear it (attached to chest via a sticky patch) once every 3 months and to record their daily ECGs for thirty days, starting with immediate use after ablation (discharge, 3, 6, 9 and 12 months). The device also has the capability of recording rhythm strips in addition to continuous recordings by study participants if/when they experience any signs or symptoms of an arrhythmia.

BodyGuardian® MINI Plus devices for all patients will be sent directly from Preventice to the trial sites before patient enrollment. After cardiac ablation, a research member will instruct the patient on how to use the device. Once the 30-day monitoring period is over, the patient will be instructed to return that device to Preventice via a pre-paid shipping label.

At the 3-month and 12-month in-person visits, a research member will provide the participant with another device. Again, once the 30-day monitoring period is over, participants will send their devices back to Preventice via a pre-paid shipping label.

At the 6- and 9-month period, sites may ship participants devices to their preferred address (sites will be responsible for creating a shipping label). Once the 30-day monitoring period is over, participants will send their devices back to Preventice via a pre-paid label.

It is important to note that at these periods if devices are shipped to a participant address, the label must be removed (to remove any identifying information) before sending it back to Preventice.

The device must be worn for the entire period and can be worn during exercise and during showering/bathing. Each patient will be assigned a unique identifier associated with the device at the participating site so that the patient's ECG transmissions will always be linked with their study participant ID. The readings from the strips will be uploaded directly onto the patient's smartphone application and sent automatically to DACIMA. Final reports will be uploaded onto DACIMA.

Trained experts blinded to treatment arm assignment at the ECG Core lab at the University of Washington, WA will be responsible for reviewing and analyzing all de-identified ECG recordings.

In the case where continuous heart monitoring may have been conducted as part of standard of care), clinical staff will upload the summary report onto DACIMA.

Patients will be informed that ECG rhythm strips and associated results are not read in real-time. If any readings are positive for AF or patients experience any AF related symptoms, they are advised to seek immediate medical attention.

Preventice has a stoplight notification protocol that allows them to identify critical and serious rhythm patterns. In this case, if such a rhythm is detected, Preventice may call sites to alert them that a participant should be immediately contacted.

Each site will create a master list that associates a participant with their device for emergency circumstances. It will be the sites responsibility to contact the participant and advise them to seek medical attention, if necessary.

### *In Between ECG Monitoring*

Although not mandatory, participants will be encouraged to provide ECG data from any other personal device. For example, a smartwatch, Holter monitor, etc. This data collection will be from time points in between regularly scheduled ECG monitoring (i.e., in between 3,6,9- and 12-months). Patients may provide data sets to their site coordinator via email or at their in-person visits.

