## **Study Design**

---

EDORA is a multicenter, prospective, phase IV, randomized, and single-blinded clinical trial.

Patients with AF undergoing ablation will be stratified by age (>65 years and <65 years) and type of atrial fibrillation (paroxysmal and persistent). Upon stratification and ablation, they will be randomized to one of two trial groups. They will either receive dronedarone (i.e. Multaq®) 400mg BID (treatment group) or placebo (control group). The control group will be started on placebo and physicians will be advised to limit the initiation of AADs to essential cases only, avoiding amiodarone and dronedarone.

Each patient will receive a pre-ablation CMR scan to assess the extent of atrial fibrosis present, followed by scans at 3 and 12-month post-ablation. QoL changes will be evaluated from baseline and again at 3 months and 12-months via the AF Effect on QualiTy of life (AFEQT) questionnaire form. frequency, duration, and severity of an AF episode, if present will be evaluated from baseline and again at 3 months and 12-months via the Atrial Fibrillation Severity Scale (AFSS) questionnaire form.

Patients will be followed post-ablation for AA recurrence (atrial fibrillation, atrial flutter, or atrial tachycardia) and will receive continuous ECG monitoring via a 30-day ECG wearable monitoring device starting at discharge, then again at 3, 6, 9- and 12-months post-ablation. Patients will also be encouraged to use any personal devices that provide ECG readings (e.g. smartwatch, etc.) in between the study timepoints and to share this data with the corresponding research team.

Phone calls or study visits will be scheduled at the study participants' 6- and 9-month mark to assess for medication compliance, changes to their medical histories, medication history, and adverse event

Page 11 of 49

Version 4.0:  
Revision Date: April 27th, 2022

Copyright© April 2022 Tulane University School of Medicine, Academic Research Organization on behalf of the Principal Investigator.  
All rights reserved.

TULANE UNIVERSITY  
Academic Research Organization

reporting as well as to assess that all study devices are working accordingly. Evaluation as to whether a patient has reached any trial endpoints will also be analyzed at this time.

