#### **1) Post-ablation AA recurrence**

Monitoring will start upon discharge, usually 24-48 hours after AF ablation.

Defined as:

- a) Time to first AA episode lasting > 30 continuous seconds, after cardiac ablation (including tachyarrhythmias presented during the 90-day post ablation blanking period).

This will be recorded by either the occurrence of a single positive AA ECG reading on the BodyGuardian® MINI Plus EL ECG monitoring study device, a 12-lead ECG, Holter monitor, or other ECG monitoring device. If there are technical difficulties or accessibility issues using the study device, patients can be monitored for AA throughout the trial via a 12-lead ECG or other heart monitoring device if necessary.

- b) New AAD initiation for AF recurrence after AF ablation, including initiation of the treatment during the blanking period, or with no available positive ECG reading.

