### *Blinding*

This is a single blinded clinical trial. Therefore, study participants will be unaware as to whether they are receiving drug or placebo. Site investigators cannot be blinded to the treatment administered since these site investigators may also be medically treating the study participant at the same time. Site investigators will need to be fully aware of the medications and associated dosages administered to their study participants to maximize study participant safety. To mitigate bias, independent ECG rhythm readers and CMR scan readers will not have access to the patient's treatment arm. In addition, all investigators, study monitors, medical monitors, data analysts, and the study team may have access to information related to the treatment arms when required.

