### *Study Duration and Close Out*

This study will span 13 months with the study participant receiving 12 months of study drug plus an additional one month of continuous ECG monitoring. In other words, approximately 13 months will be for follow-up after the last patient has been randomized into a treatment arm.

An additional 6 months is needed for data cleaning and validation, analysis, and other close out activities such as manuscript preparation.

Tulane University ARO may keep trial related information (e.g. biological sample results, ECG readings and reports, MRI scans and reports) for up to 7 years after the end of the clinical trial.

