#### End of Trial (EOT) Phone Call (Day 395 ± 30)

- Review medical history and study outcomes.
- Assess for changes in study medication.
- Assess medication compliance.
- Assess compliance/troubleshoot for study devices.
- Assess for any adverse events.

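### The atrial arrhythmia (AA) co-primary counts episodes found on any ECG device, and no planned analysis separates scheduled detection from opportunistic detection at sites that know the arm

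*Combined protocol and SAP*

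**What the plan says.** The section on post-ablation AA recurrence (Primary Endpoints) counts a single positive reading on the study monitor, "a 12-lead ECG, Holter monitor, or other ECG monitoring device". The section Definition of Trial Outcome using ECG Device repeats the any-device rule and asks for at least one tracing. New antiarrhythmic drug (AAD) initiation for AF recurrence, even without a positive ECG, and repeat ablation without a recorded episode also count as recurrence.

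Under Study Design, patients "will receive continuous ECG monitoring via a 30-day ECG wearable monitoring device starting at discharge, then again at 3, 6, 9- and 12-months post-ablation". Outside those windows there are two other routes:

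- **Personal devices.** The section In Between ECG Monitoring says "Although not mandatory, participants will be encouraged to provide ECG data from any other personal device" and "Patients may provide data sets to their site coordinator via email or at their in-person visits".
- **Standard-of-care continuous monitoring.** Here "clinical staff will upload the summary report onto DACIMA" (BodyGuardian section).

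On blinding, "Site investigators cannot be blinded to the treatment administered". Participants are blinded. The BodyGuardian section gives review of all de-identified ECG recordings to a core lab that is blinded to arm.

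The section Analysis of AF Recurrence plans Kaplan-Meier curves, a log-rank test and Cox models. The missing-data text under Analysis of LA Fibrosis Progression says that interval-censored methods will be considered for robustness. Nothing in the analysis sections distinguishes events by how they were detected.

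**The concern.** Time to first AA depends on how hard one looks. The five windows are the same in both arms. Between them, whether a 12-lead ECG or Holter is ordered, a patient is prompted to send watch tracings, or a file is forwarded can depend on staff who know the arm.

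The protocol accepts both premises. Its Randomization section places randomization after ablation because knowledge of the arm could change what investigators do. Its sample size section expects recurrent 30-day monitoring to yield more events than monitoring at a few visits.

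The imbalance could run either way. More looking in patients known to be on placebo would produce an apparent benefit with no true effect. More looking in patients known to be on dronedarone would hide a true one. Appendix C, section 5.2, gives clinicians a reason for rhythm monitoring in treated patients, although the scheduled windows may already meet it. As planned, the analysis could not show whether either had happened.

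**Working it through.** **1. The plan's own figure.** Inputs from Sample Size Estimation: 50% recurrence in controls, 33% relative reduction, 165 per arm, two-sided alpha 0.05.
- Dronedarone rate = 0.50 × (1 − 0.33) = 0.335.
- Events = 165 × (0.50 + 0.335) = 137.8, so 138.
- HR = ln(1 − 0.335)/ln(1 − 0.50) = 0.589.
- Freedman power = Φ(√138 × (1 − 0.589)/(1 + 0.589) − 1.96) = 86.0%.

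The stated 138 events and 86% power reproduce.

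**2. Calendar covered by the scheduled windows.** "This study will span 13 months with the study participant receiving 12 months of study drug plus an additional one month of continuous ECG monitoring", and the end-of-trial call is at nominal Day 395.
- Inside windows: 5 × 30 = 150 days, and 150/395 = 38.0%.
- Outside: 60 + 60 + 60 + 65 = 245 days, and 245/395 = 62.0%.
- Read literally, the voluntary collection period runs only between months 3, 6, 9 and 12: 60 + 60 + 65 = 185 days, and 185/395 = 46.8%. The any-device rule still applies to all 245 days.

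Visits have ±30-day windows, so these are nominal figures. The Schedule of Events gives the 13-month call as Day 365 ± 30, which must be reconciled with Day 395 ± 30.

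**3. Effect of unequal detection (assumed size).** Suppose no true effect, 50% detected on dronedarone, and a proportion c detected in controls because of extra looking.
- Apparent HR = ln(0.50)/ln(1 − c).
- Expected z = ln(HR) × √(events/4).
- Chance of a false benefit = P(Z < −1.96) around that mean.

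| Extra points in controls | c | HR | Events, 165 per arm | False benefit | False benefit, 132 per arm |
|---|---|---|---|---|---|
| 0 | 0.500 | 1.00 | 165 | 2.5% | 2.5% |
| 2.5 | 0.525 | 0.931 | 169 | 6.7% | about 6% |
| 5 | 0.550 | 0.868 | 173 | 15.2% | about 13% |

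The last column takes the plan's 20% loss and lets those patients contribute no events (165 × 0.8 = 132).

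**4. Cross-check by simulation.** The set-up was 165 per arm, no true effect, 55% of patients susceptible with a mean of 2 or 4 episodes each (assumed), and 1,000 runs per setting. Every in-window episode was detected. The two-sided log-rank rejection rate was:
- about 4–5% with out-of-window detection of 30% in both arms
- about 8–9% with 30% versus 15%
- about 10–15% with 50% versus 25%

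Almost all the excess favoured the arm with less detection.

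**5. Power of a scheduled-window analysis.** The share of events found only outside windows is not in the documents, so a range is assumed, with HR 0.589 and the Freedman formula:
- 0% lost: 138 events, 86%.
- 10% lost: 124 events, 82%.
- 20% lost: 110 events, 78%.

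The base of 138 counts all 165 patients per arm. A smaller base would lower these figures.

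**The case against.** The case against is substantial, and much of it stands.

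- **Participants are blinded.** A reader might infer that patients' own device habits bias the comparison. The documents do not support that. Encouragement applies to both arms, so personal use should differ by arm only through symptoms, side effects or selective prompting by sites. Discretionary monitoring by unblinded sites is the stronger route.
- **The core lab is blinded and is assigned all de-identified recordings.** The outcome definition also asks for a tracing, so a summary report alone arguably does not qualify. It would be too strong to say that outside events escape blinded review. What remains is that no step is written for sending personal-device files from the coordinator to the core lab, and that standard-of-care monitoring is described as arriving in summary form. Blinded reading also cannot correct unequal looking.
- **62% is calendar time, not share of events.** A reader might take it as the fraction of the endpoint open to bias. The first window opens at discharge, and a cited trial of short-term AAD use had 48% recurrence at 3 months. AA missed in a gap may be caught in the next window, which moves a date rather than creating an event.
- **The error rates rest on an assumed imbalance.** Ten extra points in controls would give 46.8% (about 39% with 20% loss). A reader might quote that as the trial's false-positive risk. It is not. It requires one control in ten to be counted solely through extra looking, and it concerns one of two co-primaries that must both succeed.
- **Interval-censored methods are mentioned.** They address when an episode is dated, not which source found it, and they are only to be considered.

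**Conclusion.** The concern holds in a limited form. The any-device rule, unblinded sites and 245 nominal days outside the scheduled windows leave room for detection effort to differ by arm, and no planned analysis would reveal it. The documents do not show that an imbalance will occur, how large it would be, or which arm it would favour.

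The figures of about 7% and 15% (about 6% and 13% with 20% loss) show that a modest imbalance would matter for this co-primary. They assume no true effect, proportional hazards, 50% detected on dronedarone and extra detection in controls only. They are not expected values. Requiring both co-primaries limits what they mean for the trial as a whole.

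Nothing here invalidates the primary definition. The case is for an inexpensive safeguard. Confidence is medium, because the share of first events found only outside the windows is unknown.

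**What to change.** Keep the primary analysis and make three additions.

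1. **Sensitivity analysis (Analysis of AF Recurrence).** Prespecify time to first AA in which an ECG event counts only if it comes from a core-lab-read recording within the five scheduled windows. Include substitute monitors worn in a window because of the technical or access problems that the endpoint definition allows; otherwise those patients would look event-free. State that AAD-start and repeat-ablation events are handled as in the primary, then repeat the analysis with ECG events only. Read the two together, because treatment begun after an out-of-window detection can suppress later in-window AA.
2. **Reporting by arm.** Give the number of out-of-window recordings and the source of each first event.
3. **Clarification (BodyGuardian and In Between ECG Monitoring sections).** State that the blinded core lab confirms a standard-of-care or personal-device event from the de-identified tracing. Report by arm any site-reported event with no retrievable tracing. This secures classification only. Unblinded sites would still retrieve the tracings, so the first two additions are the ones that address unequal looking.

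The cost is protocol wording, one case report form field for event source, some extra core-lab reads and additional model runs. The power of the primary is unchanged; only the sensitivity analysis has less, as in step 5 of the working. None of this closes the unblinded AAD-start and repeat-ablation routes into the endpoint.

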### *Definition of Trial Outcome using ECG Device*

The trial outcome is defined by at least one ECG tracing indicating AA for >30 seconds. AA demonstrated by any ECG device can include AA occurrence during the 90-day blanking period.

If a repeat ablation is performed, but there is no AA recurrence demonstrated by ECG readings from SOC ECG device or any other ECG device, AA recurrence will be inferred for the purposes of the primary study analysis and assigned to the date of the repeat ablation.

Page 24 of 49

Version 4.0:  
Revision Date: April 27th, 2022

Copyright© April 2022 Tulane University School of Medicine, Academic Research Organization on behalf of the Principal Investigator.  
All rights reserved.

TULANE UNIVERSITY  
Academic Research Organization

### *Stratification, Randomization and Blinding*

After cardiac ablation, trial staff will stratify each participant by age (< or  $\geq$  65 years old) and type of AF (persistent or paroxysmal). After stratification, study participants will be randomized using a web-based randomization service. Other confounding variables will be adjusted for primary outcome's analysis, including UTAH fibrosis staging. As this is a single-blind trial, only patients will be blinded to the assigned treatment arm.

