In trials reporting on an arrhythmia-free survival after catheter ablation, AADs were stopped after the initial 90-days of blanking period. The blanking period is a 3-month period post-ablation, where signs of early tachyarrhythmias due to the inflammatory nature of the procedure may be seen in some patients. This may provide predictive evidence that late tachyarrhythmias could develop and suggest failure in ablation. However, no significant evidence has been found and guidelines suggest against re-ablation during this window period. A recently published randomized controlled trial (POWDER-AF) evaluated whether continued use of previously ineffective AADs beyond the blanking period reduces arrhythmia recurrence after catheter ablation. This trial showed that in patients who were free of AF during the blanking period and continued the use of their AAD ablation had significantly less tachyarrhythmia recurrences as compared to patients who stopped their drug therapy altogether in a 12-month follow up after randomization. This observation might be explained by the possible influence of specific AADs on the atrial arrhythmogenic substrate, reducing the initiation and triggering of AF.

Left atrial (LA) fibrosis quantified through Delayed Enhanced Cardiac Magnetic Resonance Imaging (DE-MRI) represents a clinically effective tool for assessing the extent of atrial arrhythmogenic substrate. It has been shown to be a significant predictor of AF ablation success and major cardiovascular and cerebrovascular events in AF patients. [name] et al. characterized the severity of AF patients' fibrosis using Utah Stage 1-4 classification. [stage I (<10%), stage II (10-20%), stage III (20-30%) and stage IV (>30%)]. They reported a 6% AF recurrence risk post-ablation for every 1% increase in LA fibrosis from baseline values. Therefore, new fibrosis formation appears to be a novel marker of long-term ablation procedure outcomes. The generation of new fibrosis occurring post-ablation has also been associated with a significantly higher risk of atrial arrhythmia recurrence. Kheirkhahan's study also provides evidence that a 1% increase in fibrosis post-ablation increases the risk of AF recurrence by 3%.

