All CMR images will be uploaded to Marrek, Inc., (Salt Lake City, UT) Merisight portal as they arrive from each clinical trial site. If the imaging specialist believes the baseline image does not meet quality standards, they will not be further processed. Therefore, the patient will be excluded from the EDORA trial. CMR scans will be uploaded onto the Merisight portal. Any reports in addition to the CMR scanned images will help to aid in Marrek's calculations and analysis.

Marrek, Inc., will analyze and process the images, verifying that the patient has a proportion of atrial fibrosis (not limited to advanced stage fibrosis). Utah Stages 1-4 will be used to classify patients based on the percentage of fibrosis. Access to Merisight will also be granted to additional analysts who will separately determine LA and LV function and strain and aid in MRI sequencing.

A final report from Marrek Inc. will be uploaded onto Merisight's portal and uploaded onto DACIMA. All CMR scans will maintain identifying information to allow trial sites to verify that returned reports match the patients submitted identified information.

Baseline, 3 months, and 1-year CMR scans for 330 study participants will be pulled from Phillips IntelliSpace Picture Archiving and Communication System (PACS) and stored on DACIMA. All segmentations and images will also be stored on our encrypted server.

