## C. Analysis of the co-primary endpoints

### *Analysis of AF Recurrence*

Time-to-event-analysis will be conducted for AF recurrence. Patients with unobserved AF events during the study trial due to loss-of-follow-up/death or termination of the study will be treated as censored and the time to first AF recurrence will be treated as the outcome. Cumulative AF rates will be calculated by intervention conditions using the Kaplan-Meier (KM) method and compared using the log-rank test. Stratified KM curves will also be performed by Utah Stages at baseline (separate strata for Utah stages I - II, and III - IV) to investigate if the treatment effects vary across different stages. Cox proportional hazards models will be used to assess the intervention effects on the time to AF recurrence after discharge from the procedure. The proportional hazards assumption will be tested by means of graphical methods and statistical tests of lack of fit.

Due to the nature of the randomization in the study design, it is expected that the demographic characteristics and other important clinical factors will be balanced between the two groups. However, in addition to the primary predictor and the intervention condition, potential confounders will also be included in the model.

Due to the clustering effects at a physician level, we will include random effects of the physician in the model. We will also further investigate if the intervention effects are similar across the stages after controlling potential confounding effects by including the interaction of the intervention and the Utah stage in the models. In all the models, the estimated hazard ratio between the treatment and control groups with its 95% confidence interval will be provided.

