### *Analysis of LA Fibrosis Progression*

The primary outcome variable will be changes in the percentage of fibrosis from baseline, 3- and 12-months via CMR assessments in patients randomized to receive dronedarone vs. placebo.

We will apply models for longitudinal data to analyze the LA fibrosis progression over the follow-up period. The two most popular approaches for longitudinal data are the Linear Mixed-effects Model approach (LMM) and Generalized Estimating Equations (GEE). The LMM requires parametric assumption such as, normality on the random effects and model errors, and it is more powerful when the assumptions are met, but vulnerable to departures from the assumed distributions. GEE provides robust

estimates because it does not require any distribution assumption. Therefore, we will first investigate the distribution of the outcome, and if the distribution assumption is reasonable, we will use LMM model, otherwise, we will use GEE approach. Due to the clustering effect at a physician level, we will use random effects in LMM or working correlation in GEE model to account for the correlations. In all the models, the primary predictor is the intervention condition. We will also consider controlling other potential confounders if the data exhibits any. The intervention effect is assessed by the estimated coefficient of the primary predictor. The coefficient with right direction and a p value  $<0.05$  indicates there is a significant intervention effect.

Per standard principles, the primary analyses will be done on an intention to treat basis (ITT), treating all randomized patients with available outcome data regardless of compliance. A Robustness Analysis will include a per protocol analysis, where only those patients who actually received their assigned treatment (e.g., those who received dronedarone per the dosing protocol) will be analyzed. In terms of missing data, the survival analysis approach to the AF recurrence outcome will censor any patients who drop out of the study without AF recurrence at the time of their last known contact. While we would propose such patients to have their first documented recurrence date counted as their failure date, alternative analysis approaches for the analysis of interval-censored data will also be considered for robustness.

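### Baseline LA fibrosis is measured as a percentage, but the recurrence analysis names it only as Utah stage and the fibrosis model names no baseline fibrosis covariate; pre-specifying the continuous percentage in both is a small, free gain

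*Combined protocol and SAP*

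**What the plan says.** The section on baseline CMR quantification expresses left atrial fibrosis as a volumetric percentage of wall enhancement. The CMR Protocol section derives the stage from it: "Utah Stages 1-4 will be used to classify patients based on the percentage of fibrosis". The Background puts the stage boundaries at 10%, 20% and 30%.

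The Stratification, Randomization and Blinding section stratifies on age and AF type only, then says: "Other confounding variables will be adjusted for primary outcome's analysis, including UTAH fibrosis staging". The number of stage levels in the model is not given.

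In Analysis of AF Recurrence, stage appears twice. The stratified Kaplan-Meier curves use two groups ("separate strata for Utah stages I - II, and III - IV"), and effect modification is examined by "including the interaction of the intervention and the Utah stage in the models". Beyond that, "potential confounders will also be included in the model", without naming them.

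In Analysis of LA Fibrosis Progression, "The primary outcome variable will be changes in the percentage of fibrosis from baseline, 3- and 12-months". That section does not mention Utah stage and names no baseline fibrosis covariate. Other confounders are to be considered if the data suggest any. General Considerations for Data Analysis adds that baseline variables found to be imbalanced will enter the regression models.

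No section names the continuous baseline percentage as a covariate.

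**The concern.** The protocol's rationale is a per-point gradient: "They reported a 6% AF recurrence risk post-ablation for every 1% increase in LA fibrosis from baseline values". A model that uses stage treats everyone within a 10-point band alike, although the data to separate them are already in the database. Three consequences are possible.

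- **Power.** Recurrence is the endpoint that drives the sample size, and success requires both co-primary endpoints.
- **Chance imbalance.** Fibrosis is not balanced by design, so covariate adjustment is the main protection. Imbalance within a stage is not corrected by adjusting for stage.
- **Pre-specification.** The plan leaves open whether baseline fibrosis enters as a percentage, four stages or two bands, and in the fibrosis model whether it enters at all.

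**Working it through.** **1. The plan's own recurrence figure.** The inputs, from the Atrial Arrhythmia (AA) Recurrence section, are 50% one-year recurrence on control, a 33% relative reduction (so 0.50 × 0.67 = 33.5%), 165 per arm and two-sided α = 0.05.

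- Exponential hazard ratio: ln(1 − 0.335) / ln(1 − 0.50) = 0.589.
- Events: 330 × (0.50 + 0.335) / 2 = 137.8, which gives the stated 138.
- Freedman power: Φ(√138 × (1 − 0.589)/(1 + 0.589) − 1.96) = 86.0%, matching the stated 86%. Schoenfeld's formula gives 87.6%.

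The check below uses this event count as it stands, with no loss to follow-up.

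**2. Spread of risk within one stage.** Reading the 6% per point as a hazard ratio of 1.06 between patients, the hazard ratio across a 10-point band is 1.06^10 = 1.79. This compares the two ends of the band.

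**3. Effect on recurrence power.** The documents give no baseline fibrosis distribution, so four gamma distributions are assumed. Cox models were simulated (2,500 trials per row, 165 per arm, marginal rates of 50% and 33.5%, hazard ratio 1.06 per point). All four models were fitted to the same simulated trials.

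| Assumed mean/SD (points) | Fibrosis variance kept: 4 stages / 2 bands | Power, unadjusted | 2 bands | 4 stages | Continuous |
|---|---|---|---|---|---|
| 15/6 | 82% / 57% | 88.4% | 88.8% | 89.1% | 89.8% |
| 18/5 | 75% / 63% | 87.2% | 87.8% | 87.6% | 88.2% |
| 18/8 | 86% / 64% | 87.0% | 89.5% | 90.6% | 90.6% |
| 20/10 | 86% / 62% | 87.5% | 89.9% | 91.3% | 92.6% |

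Continuous adjustment gains 0.0 to 1.3 points over four stages and 0.4 to 2.7 points over two bands. The Monte Carlo standard error is about 0.6 points per figure. The data were generated with a log-linear fibrosis effect, which favours the continuous model. In the 18/5 row the average four-stage estimate was not finite, so that cell is less secure. The end stages there hold only 3.3% and 1.8% of patients, and 330 × 0.018 is about 6.

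**4. Precision of the hazard ratio.** A further simulation on the same inputs (distributions 15/6, 18/8 and 20/10) gave a median standard error of the log hazard ratio of 0.174–0.175 unadjusted, 0.175–0.176 with four stages and 0.175 continuous. What moves is the estimate: across the table's scenarios the average treatment hazard ratio is 0.582–0.587 unadjusted and 0.548–0.579 with continuous adjustment.

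**5. Chance imbalance.** Assume an SD of 8 points. The 95% limit for a chance difference in mean fibrosis is 1.96 × 8 × √(2/165) = 1.73 points, and 1.06^1.73 = 1.11. Using the variance shares in the 18/8 row:

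- Four stages: residual SD 8 × √(1 − 0.864) = 2.95, limit 1.96 × 2.95 × √(2/165) = 0.64 points, factor 1.06^0.64 = 1.04.
- Two bands: residual SD 8 × √(1 − 0.640) = 4.80, limit 1.04 points, factor 1.06^1.04 = 1.06.

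**6. Fibrosis endpoint.** The Atrial Fibrosis Progression section assumes a 10% mean, a 20% reduction (2 points), an SD of 1.59 and 86 patients with 20% dropout, so about 34 per arm. Power is Φ(2 / (1.59 × √(2/34)) − 1.96) = 99.9%, which reproduces the stated figure of more than 99%. With 330 patients it is effectively 100%, leaving no room for a power gain.

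**The case against.** A fair defence has five parts.

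- **The covariate list is open.** The adjustment sentence is inclusive, the recurrence section allows further confounders, and imbalanced variables are to be added. A reader might infer that stage is the sole permitted form. The text does not say so; it is only the sole form named. This answer stands, but selecting covariates on observed imbalance does not replace a pre-specified form.
- **The fibrosis model does not use stage.** A reader might infer that banding affects both co-primary models. It does not. The gap there is that no baseline fibrosis covariate is named. Moreover, the section on the twelve-month CMR takes the three-month scan as the reference for new fibrosis, so under that definition the pre-ablation value is not the one subtracted and the usual change-score argument applies less directly.
- **Two-band adjustment is not stated.** The I–II versus III–IV split is given only for Kaplan-Meier curves, which need groups. The two-band figures above are therefore a bound, not a description of the planned model.
- **The gradient is ambiguous.** The 6% is worded as an increase from baseline values, which could mean change within a patient. If so, 1.79 does not describe differences between patients at baseline, and the power gain could be smaller.
- **Stage is established and interpretable.** Reporting by Utah stage is legitimate, and a continuous term brings a linearity assumption.

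What remains is that the percentage is available, its use is not specified, and it carries at least as much information as the stage derived from it.

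**Conclusion.** The point holds as a modest improvement in efficiency and pre-specification. For recurrence the gain is roughly 0 to 1.5 points of power over four stages and up to about 3 points over two bands, together with tighter control of chance imbalance in a factor not used in randomisation. For fibrosis progression there is no demonstrable power gain on the stated inputs; the benefit is imbalance control. These sizes rest on assumed baseline distributions, on a between-patient hazard ratio of 1.06 per point, and on the plan's 138 events.

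Three stronger readings are not supported. The protocol calls fibrosis a significant and a strong predictor but does not rank it above other factors. Continuous adjustment should not be expected to narrow the Cox interval: the hazard ratio is non-collapsible, so the estimate moves away from 1 while its standard error stays about the same. Explained-variance arithmetic from linear models does not carry over to the censored endpoint. Nor does staging threaten validity: with randomised allocation it creates no bias or type I error problem.

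**What to change.** In Stratification, Randomization and Blinding, Analysis of AF Recurrence and Analysis of LA Fibrosis Progression, name the pre-ablation LA fibrosis percentage as a continuous covariate in the Cox model and in the fibrosis model. In the fibrosis model it should enter as a covariate and not also as a repeated outcome value. Test effect modification with the interaction of arm and the continuous percentage. Keep the Utah-stage Kaplan-Meier curves and stage-specific results for display.

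The cost is wording, settled before database lock; no new data, visits or patients are needed. The small downside is the linearity assumption, so pre-specify a check, for example with a spline, and say what will be done if it fails.
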